**Table 11 - Time window for pharmacokinetics/pharmacodynamics variables**

Analysis visit	Target day	Time windows for				
		Serum dupilumab, ADA	Blood biomarkers	Urine biomarkers	Nasal secretions for protein biomarkers	Nasal brushing for RNA and cytology
Screening	-28 to -14					
Baseline	1	<1-	<1-	<1-	<1-	<1-
Week 2	15					
Week 12	85	1 + -126	1 + -126	1 + -126	1 + -126	
Week 24	169	127-266	127-266	127-266	127-266	1 + -266
Week 40	281					
Week 52	365	>266	>266	>266	>266	>266
EOS*	NA	NA				

1: up to randomization and before 1st dose date/time; 1+: after randomization or 1st dose date/time

\*PK and ADA data collected at the EOS visit will not be remapped

## Unscheduled visits

Unscheduled visit measurements of laboratory data and vital signs will be used for computation of baseline, the last on-treatment value, analysis according to PCSAs, and the shift summaries for safety. They will also be included in the by-visit summaries if they are re-allocated to scheduled visits. Uncheduled visit measurements for efficacy data will be included in the by-visit summaries if they are re-allocated to scheduled visits.

## 5.5 APPENDIX 5 SELECTION CRITERIA FOR AE GROUPINGS

Table 12 - List of PTs for CMQs

Grouping	Preferred Term Code	Preferred Term
Conjunctivitis	10001257	Adenoviral conjunctivitis
Conjunctivitis	10010725	Conjunctival irritation
Conjunctivitis	10010726	Conjunctival oedema
Conjunctivitis	10010736	Conjunctival ulcer
Conjunctivitis	10010741	Conjunctivitis
Conjunctivitis	10010744	Conjunctivitis allergic
Conjunctivitis	10010745	Conjunctivitis chlamydial
Conjunctivitis	10010749	Conjunctivitis gonococcal neonatal
Conjunctivitis	10010754	Conjunctivitis tuberculous
Conjunctivitis	10010755	Conjunctivitis viral
Conjunctivitis	10018258	Giant papillary conjunctivitis
Conjunctivitis	10021629	Inclusion conjunctivitis
Conjunctivitis	10030861	Ophthalmia neonatorum
Conjunctivitis	10048908	Seasonal allergy
Conjunctivitis	10049458	Herpes simplex virus conjunctivitis neonatal
Conjunctivitis	10051625	Conjunctival hyperaemia
Conjunctivitis	10053991	Inclusion conjunctivitis neonatal
Conjunctivitis	10061784	Conjunctivitis bacterial
Conjunctivitis	10062889	Pingueculitis
Conjunctivitis	10063669	Photoelectric conjunctivitis
Conjunctivitis	10067317	Oculorespiratory syndrome
Conjunctivitis	10067817	Acute haemorrhagic conjunctivitis
Conjunctivitis	10069166	Blebitis
Conjunctivitis	10071570	Ligneous conjunctivitis
Conjunctivitis	10074701	Noninfective conjunctivitis
Conjunctivitis	10075264	Oculoglandular syndrome
Conjunctivitis	10080825	Conjunctivitis fungal
Conjunctivitis	10084034	Conjunctival suffusion

Signature Page for VV-CLIN-0662822 v1.0  
efc16723-16-1-9-sap

Approve & eSign

Clinical

Approve & eSign

Clinical

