Consistent with the implication of type-2 inflammation underlying the disease process in these CRS patients, asthma is a common comorbid condition for both CRSsNP and CRSwNP patients: 20% to 40% in the former and 50% to 60% in the latter (4, 11), and about 52% of CRSsNP patients are reported to have comorbid allergic rhinitis (4). Fractional exhaled nitric oxide has been reported to be significantly correlated with other markers of type-2 inflammation, including elevated peripheral blood eosinophil counts and tissue eosinophilia, which also correlates with LMK scores in patients with CRS (27). Fractional exhaled nitric oxide has been noted to be elevated in CRSwNP patients with tissue eosinophilia independent of a diagnosis of asthma (27). Further peripheral blood eosinophilia,  $\geq 300$  cells/mm^3 (sensitivity 70%, specificity 70%), has been reported as a predictor of bronchial hyperresponsiveness in CRSsNP patients without a diagnosis of asthma (22). Comorbid asthma and peripheral blood eosinophilia have been associated with a higher risk of need for recurrent sinonal surgery and need for systemic therapy after sinus surgery (12, 13, 28). Other clinical features more commonly reported in CRSsNP patients with type-2 endotype include loss of sense of smell/reduced taste; the type-2 CRSsNP patients also have more complaints of headache/migraine as compared with the non-type-2 CRSsNP patients (5).

The pathological hallmark of CRSsNP-associated upper airway disease is mucus secretion and goblet cell and glandular hyperplasia. Goblet cells are responsible for the production of mucin 5AC, one of the main secreted mucins in the human airway (29). The increase in mucous gland density that occurs in patients with severe CRSsNP is in contrast to those with CRSwNP who show a significant decrease in mucous gland density (30, 31, 32, 33). Glandular hypertrophy and mucous secretion in the airway mucosa are likely to be mediated by various cytokines, including IL-13 (34, 35, 36).

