### 8.3.6 Adverse event of special interest

#### Adverse event of special interest

An adverse event of special interest (AESI) is an AE (serious or nonserious) of scientific and medical concern specific to the Sponsor's product or program, for which ongoing monitoring and immediate notification by the Investigator to the Sponsor is required. Such events may require further investigation in order to characterize and understand them. Adverse events of special interest may be added, modified, or removed during a study by protocol amendment.

For these AESIs, the Sponsor will be informed immediately (ie, within 24 hours), per SAE notification described in [Section 10.3](#), even if not fulfilling a seriousness criterion, using the corresponding pages in the eCRF (to be sent) or screens in the eCRF. Adverse event of special interests for this study include:

- Anaphylactic reactions.
- Systemic hypersensitivity reactions.
- Helminthic infections.
- Any severe type of conjunctivitis or blepharitis.
- Keratitis.
- Clinically symptomatic eosinophilia (or eosinophilia associated with clinical symptoms).
- Pregnancy of a female participant entered in a study as well as pregnancy occurring in a female partner of a male participant entered in the study with IMP:
  - Pregnancy occurring in a female participant entered in the clinical trial or in a female partner of a male participant entered in the clinical trial will be qualified as an SAE only if it fulfills one of the seriousness criteria,
  - In the event of pregnancy in a female participant, IMP should be discontinued,
  - Follow-up of the pregnancy in a female participant or in a female partner of a male participant is mandatory until the outcome has been determined,
  - Abnormal pregnancy outcomes (eg, spontaneous abortion, fetal death, stillbirth, congenital anomalies, ectopic pregnancy) are considered SAEs.

- Significant ALT elevation:
  - ALT  $>5 \times$  ULN in participants with baseline ALT  $\leq 2 \times$  ULN,
  - OR
  - ALT  $>8 \times$  ULN if baseline ALT  $>2 \times$  ULN.
- Symptomatic overdose (serious or nonserious) with IMP/NIMP

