**Table 6 - Selections for AESIs and other AEs of interest**

AESIs and other AEs of interest	Criteria
AESI	
Anaphylactic reaction	Anaphylactic reaction algorithmic approach (Introductory Guide for Standardised MedDRA Queries (SMQs) Version 18.1): includes anaphylactic reaction narrow SMQ (20000021) terms and programmatic identification of cases based on occurrence of at least two preferred terms meeting the algorithm criteria occurring within 24 hours of each other. The latter cases identified using the algorithm will undergo blinded medical review taking into account the timing of events relative to each other and to IMP administration for final determination of an anaphylactic reaction or not.
Systemic hypersensitivity reactions	SMQ [20000214] hypersensitivity narrow search and [AE corrective treatment/therapy = 'Y' or Action taken with IMP = 'Drug withdrawn' or Action taken with IMP = 'Drug interrupted'] followed by blinded medical review (documented process) for selection of relevant systemic hypersensitivity events
Helminthic infections	CMQ10544 based on HLGT as "Helminthic disorder"
Any severe type of conjunctivitis	CMQ10498 based on PTs (See Section 5.5 a ) and "Severe" ticked in Adverse Events eCRF page
Any severe type of blepharitis	CMQ10497 based on HLTT as "Lid, lash and lacrimal infections, irritations and inflammations" and "Severe" ticked in Adverse Events eCRF page
Keratitis	CMQ10642 based on the following PTs [keratitis, allergic keratitis, ulcerative keratitis, atopic keratoconjunctivitis, herpes ophthalmic, ophthalmic herpes simplex, corneal infection] a
Clinically symptomatic eosinophilia (or eosinophilia associated with clinical symptoms) b	CMQ10641 based on HLTT = Eosinophilic disorders or PT = Eosinophil count increased followed by blinded medical review
Pregnancy of female participants entered in a study as well as pregnancy occurring in a female partner of a male participant entered in a study with IMP	"Pregnancy" or "Partner Pregnancy" checked on the Pregnancy eCRF page as reported by the investigator
Significant ALT elevation	"ALT increase" and AESI answer "Yes" checked on AE eCRF as reported by the Investigator (ALT >5 x ULN in participants with baseline ALT ≤2 x ULN; OR ALT >8 x ULN if baseline ALT >2 x ULN)
Symptomatic overdose with IMP	Symptomatic Overdose is answered Yes, with Overdose of Study Treatment answered Yes on AE eCRF.

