Symptomatic overdose with NIMP	Symptomatic Overdose is answered Yes, with Overdose of NIMP answered Yes on AE eCRF.
Other selected AE Grouping	
Serious injection site reactions or severe injection site reactions that last longer than 24 hours	HLTT = 'Injection site reactions' and either with serious status, or with severe status and (AE end date/time - AE start date/time) ≥24 hours or ongoing
Severe or serious infection	Primary SOC = 'Infections and infestations' and with severe or serious status
Parasitic infection	Infection type "Parasitic" checked on eCRF "Infection Event Form"
Opportunistic infection	Has the AE been assessed as opportunistic infection? is answered Yes on eCRF "Infection Event Form"

AESIs and other AEs of interest	Criteria
Drug-related hepatic disorder	SMQ [20000006] Drug-related hepatic disorders- narrow
Injection site reactions	HLT = 'Injection site reactions'
Malignancy	SMQ [20000091]- Malignant or unspecified tumors narrow
Conjunctivitis (narrow)	CMQ10644 based on the following PTs [Conjunctivitis, Conjunctivitis allergic, Conjunctivitis bacterial, Conjunctivitis viral, Atopic keratoconjunctivitis] a
Conjunctivitis (broad)	CMQ10645 based on the following PTs [Conjunctivitis, Conjunctivitis allergic, Conjunctivitis bacterial, Conjunctivitis viral, Atopic keratoconjunctivitis, Blepharitis, Dry eye, Eye irritation, Eye pruritus, Lacrimation increased, Eye discharge, Foreign body sensation in eyes, Photophobia, Xerophthalmia, Ocular hyperaemia, Conjunctival hyperaemia] a
Conjunctivitis █ c	CMQ10643 based on the following PTs [Conjunctivitis, Conjunctivitis allergic, Conjunctivitis bacterial, Conjunctivitis viral, Eye irritation, Eye inflammation, Giant papillary conjunctivitis] a
Keratitis █ c	CMQ30102 based on the following PTs [keratitis, allergic keratitis, ulcerative keratitis, atopic keratoconjunctivitis, ophthalmic herpes simplex] a

a The list of terms may be adjusted according to MedDRA version changes

b All cases of Eosinophilia will be included in the analysis, where cases associated with clinical symptoms will be further described in the CSR

c Labeling subgroup of preferred terms included in the USPI for Dupixent.

The following summaries will be provided:

- All TEAEs, by selected standardized MedDRA query (SMQ)/Customized MedDRA query (CMQ) and PT, showing the number (%) of participants with at least 1 PT.

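### The SAP's term list for the severe conjunctivitis AESI includes Seasonal allergy, a non-eye term that no rule removes (minor)

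*SAP*

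**What the plan says.** Protocol Section 8.3.6 names the AESI as "Any severe type of conjunctivitis or blepharitis". The SAP handles its conjunctivitis part in Section 3.6.2, Table 6. The term condition is "CMQ10498 based on PTs", with a pointer to Section 5.5. The severity condition is that Severe is "ticked in Adverse Events eCRF page". The row states nothing further.

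Section 5.5 contains a single table, "Table 12 - List of PTs for CMQs". All its entries fall under the one grouping Conjunctivitis, and one entry is PT 10048908, "Seasonal allergy".

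Table 6 also defines three other conjunctivitis groupings, each with its PTs written out in the row: narrow (CMQ10644), broad (CMQ10645) and a labeling subgroup (CMQ10643).

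**The concern.** Seasonal allergy does not describe an eye condition. Because the rule is mechanical, a severe event coded to that PT becomes a severe conjunctivitis AESI whether or not the eye was involved.

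Protocol Section 2.3.1 lists conjunctivitis among the identified adverse drug reactions of dupilumab, so this row will be read closely. A misclassified participant would also enter the any-AESI line of the TEAE overview and the AESI breakdowns by seriousness, relatedness, intensity and discontinuation. If exposure proves imbalanced between arms, the participant would enter the exposure-adjusted rates too.

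Allergic disease is common in this setting: Protocol Section 2.2 says that "about 52% of CRSsNP patients are reported to have comorbid allergic rhinitis". Worsening of a pre-existing intermittent condition can qualify as an AE under Protocol Section 10.3.1. Such an event is therefore conceivable, although nothing in the documents says how often it would occur.

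**Working it through.** No figure in the plan depends on this point, so there is none to reproduce. The check follows the selection rule through the documents and then compares term lists.

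**1. The rule, applied literally.** An event is a severe conjunctivitis AESI if its PT is in Table 12 and its severity is Severe. Seasonal allergy is in Table 12, so a severe event with that PT satisfies both conditions.

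**2. Is the term out of place in its own list?** Table 12 has 28 PTs. Most have conjunctivitis or conjunctival in the name. The less obvious ones (Pingueculitis, Blebitis, Ophthalmia neonatorum, Oculorespiratory syndrome, Oculoglandular syndrome) are still eye conditions by name or nature. Seasonal allergy is the one exception, leaving 28 − 1 = 27 eye terms.

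**3. Is it in the SAP's other conjunctivitis groupings?**

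| Grouping | PTs listed | Contains Seasonal allergy |
|---|---|---|
| Severe AESI (CMQ10498, Table 12) | 28 | Yes |
| Narrow (CMQ10644) | 5 | No |
| Broad (CMQ10645) | 16 | No |
| Labeling subgroup (CMQ10643) | 7 | No |

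The SAP also separates the concepts elsewhere: the comorbidity list in Section 5.3 has different entries for seasonal allergic rhinitis and allergic conjunctivitis.

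**4. Does anything remove the event later?**
- Medical review: Table 6 specifies blinded review for systemic hypersensitivity, for anaphylaxis cases found by the algorithm, and for eosinophilia. It specifies none for severe conjunctivitis.
- Footnote a to Table 6: it provides for updating term lists when the MedDRA version changes, which does not cover this term.
- Investigator-reported AESIs: these are summarized in a separate table, which leaves the query-based count as it is.

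**5. Size per event.** Planned arm size is about 35 (Protocol Section 4.1). One misclassified participant adds 1/35 = 0.0286, or about 2.9 percentage points, to that arm's row. This assumes that the safety population is close to the planned size.

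**The case against.** The strongest reply is that the case is narrow and the planned output would expose it. Several parts of that reply stand.

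- **Visibility.** Section 3.6.2 plans AESI counts by PT where applicable, and all TEAEs by query and PT. A Seasonal allergy event would appear under its own name, so a careful reader could identify it. The category total and the any-AESI line would still include it.
- **Likelihood.** The event must be treatment-emergent, rated Severe (which Protocol Section 10.3.3 reserves for events that stop ordinary daily activity), and coded to this exact PT. The documents do not show which reported terms code there. The 52% figure is literature on comorbid allergic rhinitis, not an event rate and not data on enrolled participants.
- **Absence of review is not unusual.** Only three of the eleven AESI rows in Table 6 mention blinded review. Blepharitis, keratitis and helminthic infection have none. The lack of review matters here only because the list holds a term that review would have caught.
- **Source of the list.** The neonatal terms in a list used for an adults-only trial suggest a query not tailored to this study. That is an inference; the documents do not say whether CMQ10498 is a standard query or why the term is in it.

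Two stronger readings are tempting, and the documents support neither.

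- A reader might infer that the broad grouping is the widest set, so that Seasonal allergy alone could let the severe count exceed the broad count. Broad has 16 PTs, ending "Foreign body sensation in eyes, Photophobia, Xerophthalmia, Ocular hyperaemia, Conjunctival hyperaemia", against 28 in Table 12. They share five: Conjunctivitis, its allergic, bacterial and viral forms, and Conjunctival hyperaemia. So 28 − 5 = 23 Table 12 terms lie outside broad, and 27 − 5 = 22 would remain outside after the correction. These are separate queries and were never nested.
- A reader might infer that the term could hide a real eye signal, for instance through placebo events. The narrow, broad and labeling groupings omit it, and the tables by PT separate it, so a true eye imbalance would still be visible.

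**Conclusion.** The point holds as a minor specification error. The rule in Table 6, combined with the list in Table 12, counts a severe event coded to Seasonal allergy as severe conjunctivitis, and nothing in the plan takes it out again.

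Each affected participant shifts the row by about 2.9 percentage points, given about 35 per arm. The number affected cannot be estimated because the documents give no rate, and it may well be zero. A picture such as no true cases against two reported in one arm (2/35 = 5.7%) would illustrate the arithmetic only; it is not a forecast.

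The effect is confined to descriptive safety tables. SAP Section 3.6 plans no safety testing, and the primary estimand, the other efficacy analyses and the sample size are untouched.

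**What to change.** Before database lock, make one of two changes:

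- Remove PT 10048908 from the list used for this AESI, leaving 27 terms. This is a one-line SAP edit.
- If CMQ10498 has to stay unchanged as a standard query, add a step to the severe conjunctivitis row of Table 6 requiring blinded medical review to confirm eye involvement, as the systemic hypersensitivity and eosinophilia rows already require review. This needs a short documented review as well as the SAP edit, and it would cover only the severe events that the list selects.

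Neither option needs new data. Making the change before unblinding matters because the same correction made afterwards could look driven by the results.
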